Official Title: Bridging Pediatric and Adult Biomarkers in Graft-Versus-Host Disease

NCT number: NCT02194439

Document date: 01Feb2020

Study population

The study accrued 415 HCT recipients between 2013 and 2018; 170 children ≤10 years and 245 subjects >10 years, including both children and adults. All subjects were followed for at least 1 year. This study registered at clinicaltrial.gov under NCT02194439 was approved by the respective Institutional Review Boards at six adult and pediatric centers: Children's National Medical Center, Texas Children's Hospital, Fred Hutchinson Cancer Research Center, Boston Children's/Dana Farber Cancer Institute, Johns Hopkins, and Indiana University. Adult patients were solely from two centers. Informed consent was btained from all patients or their legal guardians.

Samples preparation and ELISA

All plasma samples were prospectively collected and stored per institutional guidelines. Frozen samples were shipped to the [name] Laboratory at Indiana University for analysis. ST2, IL6, REG3α, and TNFR1 were measured pre-HCT (day -7) and on days +7, +14, +21 post-HCT as previously examined in the aGVHD setting. All of these biomarkers were measured using sequential enzyme-linked immunosorbent assay (ELISA), as previously reported.

Statistical analysis

Descriptive statistics of demographic variables and NRM including frequencies and percentages were summarized by age groups (≤10 years vs. >10 years). Chi-square or nonparametric Mann-Whitney tests were performed to assess potential differences in demographic variables between age categories. Cumulative incidences of NRM and aGVHD were analyzed with relapse as a competing risk. The Aalen-Johansen estimator was used to nonparametrically estimate the cumulative incidence function (CIF) of NRM and aGVHD. In order to account for the time-dependent biomarker values (pre-HCT, and at 7, 14 and 21 days post-HCT) we employed landmark analyses. Separate CIFs were estimated by biomarker category (above and below the median at day 21 for the whole cohort which is also a clinically relevant threshold based on previous studies) for each landmark time point, the biomarker value at this landmark time point was considered and, also, patients who survived until that landmark. To statistically evaluate the difference of the CIFs of NRM and GVHD between the two biomarker groups, while accounting for the left truncation at each landmark point, we used two-sample nonparametric linear tests. To perform a multivariable competing risks analysis, the biomarker values for all landmarks points were stacked into a single variable and a semiparametric proportional cause-specific hazards model was fitted to the data. Hazard ratios with confidence intervals were reported to demonstrate effect size. To account for the potential association across the repeated records for each patient we used a proper sandwich variance estimator in a population-averaged estimation framework. For each model, the interaction between the biomarker and the landmark quantified the change of the association between each biomarker and the outcome over time. If the interaction was not statistically significant then there was no evidence that the association between the biomarker and the outcome changed over time. The models also included an interaction term between the biomarker and patient's age. A significant biomarker by age interaction indicated that the association between the biomarker and the outcome differed between age groups. Multivariable analyses were conducted using the following covariates: race/ethnicity, malignant disease, graft source, and aGVHD prophylaxis. A cause-specific analysis that included type of malignant disease type, disease risk index, and disease status at HCT was also performed in the subgroup of patients with malignant diseases. We sought to determine if the combination of biomarkers improves the predictive accuracy for NRM.

To compare the predictive accuracy across different baseline biomarkers we used the time-dependent prediction error estimate proposed by Schoop et al. This measure, estimates predictive accuracy in situations with time-to-event outcomes and competing risks. A lower value of the estimated prediction error indicates a better predictive performance. A p-value of <0.05 was considered significant.

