11. APPENDIX C: STATISTICS

Sample Size and Power Calculation. Three clinical endpoints are chosen as the primary hypotheses: D180 Post Therapy non-relapse mortality, D28 post-therapy non-response, and GVHD grade 1-4 onset. Seven biomarkers will be tested at either onset of GVHD or at day 14 post-HCT (median 14 days prior GVHD) in predicting these clinical endpoints. Therefore, the overall type-I error is justified by a fact of 7*3*2 = 42, and the per comparison type I error is controlled at 0.05/42 = 0.0012. The effect size is pre-specified by the expected sensitivity and specificity of a biomarker, which ranges from 0.60 to 0.70. The following table present the power of our study (N = 350) for three clinical endpoints. It shows that we shall have more than 91% power to test our hypotheses. Given the fact that our preliminary data show that one biomarker has a 85% sensitivity and specificity, our proposed sample size will have sufficient power to test our hypothesis.

Response Type and Rate	Sensitivity and Specificity		
	0.60	0.65	0.70
D180 Post Therapy non-relapse mortality (0.26)	0.91	>0.99	>0.99
D28 post-therapy non-response (0.41)	0.96	>0.99	>0.99
GVHD grade 1-4 onset (0.50)	0.98	>0.99	>0.99

Our 'pre-specified' expected sensitivity and specificity are based on our previous work (taking the median as cutoff) (see Table below, Vander Lugt et al. NEJM, 2013)

Sonsitivity and	l snacificity of	ST2 concentrations at	D14 to predict	six-month n	ost-HCT NRM
Sensitivity and	i specificity of	SIZ CONCENTRATIONS at	D 14 to predict	six-monui p	

0.1.1	Sensitivity	Specificity
Cutoff	(95% CI)	(95% CI)
75 th percentile	54% (50-59%)	83% (77-89%)
Median	75% (71-79%)	56% (48-64%)
25 th percentile	92% (89-94%)	29% (22-36%)

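### The SAP gives relapse as the competing event for aGVHD incidence but does not cover death without aGVHD; if those deaths were censored, the aGVHD curves are too high

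*SAP*

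**What the plan says.** The SAP (Statistical analysis) sets the event structure for two endpoints in one sentence: "Cumulative incidences of NRM and aGVHD were analyzed with relapse as a competing risk". Both cumulative incidence functions (CIFs) are estimated by Aalen-Johansen at landmarks pre-HCT and at days 7, 14 and 21, among "patients who survived until that landmark". At each landmark patients are split "above and below the median at day 21 for the whole cohort", and the curves are compared: "we used two-sample nonparametric linear tests". The multivariable model uses cause-specific hazards.

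The protocol does not fill the gap. Section 3.3 defines NRM as death not due to relapse of the underlying malignancy. Appendix C gives cumulative incidence regression for NRM only, and models time to GVHD by Cox regression without naming a competing event.

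**The concern.** For NRM, non-relapse death is the event and relapse competes, so the rule is complete. For aGVHD, a patient who dies without relapse and without aGVHD can never have the event. If that death is censored, the estimator treats the patient as still able to develop aGVHD and passes the patient's weight to those who remain at risk. Landmarking removes deaths before each landmark, not deaths after it.

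The SAP adjusts for malignant disease and has a separate analysis of malignant cases, so the cohort includes non-malignant disease. For those patients relapse of a malignancy does not apply, and the stated rule leaves no competing event at all for aGVHD.

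Two things are at stake: the level of the aGVHD curves, and the comparison of the curves between biomarker groups when deaths without aGVHD are unequally distributed. That is plausible, because Appendix C links high day-14 ST2 to six-month NRM.

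**Working it through.** The plan gives no figure to reproduce here. The check has a part that is certain (direction) and a part that rests on assumptions (size).

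**Direction.** The estimate is F(t) = Σ S(u−) × d(u)/n(u), where d(u) is the number of aGVHD events at u, n(u) the number at risk and S(u−) the event-free probability. Censoring deaths or counting them as competing leaves d(u) and n(u) unchanged. Censoring only drops the death factor from S(u−), so F(t) is equal or larger at every t. In 600 simulated data sets (415 patients, landmarks 0, 7, 14 and 21, 150 each) the censored estimate was never below the correct one.

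**Inputs from the documents.**
- Appendix C, median cutoff for day-14 ST2 and six-month NRM: sensitivity 75%, specificity 56%.
- Appendix C, planning rates: post-therapy NRM 0.26, GVHD onset 0.50.
- Protocol 1.1: aGVHD typically at two to eight weeks, taken as days 14 to 56.
- SAP: 415 patients, about 207 per group.

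**Implied NRM by group.** A median split puts half the patients above the cutoff: 0.75p + 0.44(1 − p) = 0.50, so p = 0.06/0.31 = 0.194. Above the median: 0.75 × 0.194/0.5 = 29.0%. Below: 0.25 × 0.194/0.5 = 9.7%.

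**Share of NRM without aGVHD.** NRM after treated GVHD is about 0.26 × 0.50 = 0.13 of all patients, leaving 1 − 0.13/0.194 = 0.33. Clocks and cohorts differ, so shares of 25%, one third and 50% were used. Deaths without aGVHD, low versus high group: 2.4% v 7.3%, 3.2% v 9.7%, 4.8% v 14.5%.

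**Model.** Assume true 180-day aGVHD 50% and relapse 10% in both groups, constant relapse and death hazards, and an aGVHD hazard only in days 14 to 56. With landmark L, a = max(14, L), and aGVHD and relapse hazards g and r solved to give those incidences, the CIF with deaths censored is

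exp(−r(a − L)) × g/(g + r) × (1 − exp(−(56 − a)(g + r))).

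Example (L = 0, one-third share, high group): g = 0.01843 and r = 0.00118 per day give 51.87%.

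| Share | L = 0: low v high | Gap | L = 21: low v high | Gap |
|---|---|---|---|---|
| 25% | 50.42 v 51.35 | 0.93 | 50.24 v 50.78 | 0.54 |
| one third | 50.57 v 51.87 | 1.30 | 50.33 v 51.08 | 0.75 |
| 50% | 50.87 v 53.04 | 2.17 | 50.50 v 51.75 | 1.24 |

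The true gap is zero in every row. Gaps at day 7 are 0.78, 1.09 and 1.82 points; at day 14, 0.61, 0.85 and 1.41. With deaths spread evenly to day 180 they are 0.56, 0.75 and 1.15 (day 0) and 0.34, 0.45 and 0.69 (day 21).

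**Effect on a test.** With 207 per group and 4,000 replicates, a nominal 5% test on the average CIF difference to day 180 rejected in 5.8%, 5.8% and 7.1% (day 0) and 5.3%, 5.2% and 6.0% (day 21). With death as a competing event it rejected in 4.7% to 5.2%. The Monte Carlo standard error is about 0.35 to 0.4 points.

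**Level of a single curve.** If all three hazards run in proportion, deaths fall in step with aGVHD and the bias is larger. With 50% aGVHD, 10% relapse first, and 2%, 5%, 10% or 15% death first (assumed), the curve reads 50.7%, 51.7%, 53.6% or 55.8%. With relapse first at 5% to 15%, the excess spans 0.6 to 6.1 points.

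**Direction between groups.** It can reverse. In the first model at day 0, 50% aGVHD and 2% death in the high group give 0.35 points of inflation; 30% aGVHD and 5% death in the low group give 0.42.

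**The case against.** The strongest reply is that silence is not an instruction. The SAP does not call relapse the only competing risk and does not say deaths are censored. It is a short, past-tense summary that otherwise uses suitable competing-risk methods, so correct coding described too briefly is at least as plausible as wrong coding. That stands, and it is why the conclusion is conditional. What does not follow is that nothing needs changing: a reader applying the sentence to aGVHD would get the wrong estimator.

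The effect is small. That also stands. At day 21 the two smaller shares give rejection rates within simulation error of 5%.

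The inputs are rough. They are: the confidence intervals in Appendix C imply about 450 to 471 NRM events and 148 to 161 non-events, the reverse of 19% NRM. They come from a prior study with equal halves, whereas the SAP applies the day-21 median at every landmark. Day 0 only stands in for the pre-HCT landmark. The figures are illustrations; the direction argument does not depend on them.

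The link to a primary endpoint is loose. GVHD onset is listed in protocol 3.1, but for markers measured at the start of therapy, and Appendix C analyses onset by logistic and Cox regression. The SAP's landmark aGVHD curves are therefore not the protocol's stated primary analysis.

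**Conclusion.** The concern holds as a minor point. The stated rule is complete for NRM and incomplete for aGVHD. If non-relapse deaths before aGVHD were censored, the aGVHD curves are certainly at or above the true incidence, and equal to it only where no such deaths preceded. How the deaths were in fact coded is not known.

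Under the assumptions above the spurious between-group gap is roughly 0.3 to 2.2 points, with little loss of test validity, and its direction in this trial is not established. The true size cannot be computed without the number of deaths without aGVHD. Censoring competing events is standard for cause-specific hazard ratios, so those results are not in question.

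**What to change.** 1. State how death without prior aGVHD was coded.
2. For aGVHD, name relapse and death without prior aGVHD as competing events in the Aalen-Johansen estimates and the two-sample tests at every landmark. Keep relapse as the competing event for NRM.
3. Report the number of such deaths by biomarker group and landmark.
4. Re-estimate the aGVHD curves and tests only if those deaths were censored.

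The study team can check quickly. The SAP says "All subjects were followed for at least 1 year". With no loss before day 180, the correct day-180 aGVHD CIF at a landmark equals the plain proportion of at-risk patients whose first event was aGVHD. A higher reported value would then show that deaths were censored. The check fails if there was earlier censoring, for example while data collection waits for re-consent at age 18 (protocol 4.1).

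The cost is one SAP sentence and a count table, plus an event recode and rerun if needed. Non-relapse deaths are already study events, so no new data are required. Reported aGVHD incidence might fall slightly.

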1. BACKGROUND AND RATIONALE

1.1. Acute Graft-versus-Host Disease (GVHD)

Allogeneic hematopoietic cell transplantation (HCT) is a potential curative therapy for cancers of the blood and bone marrow, including leukemias that represent approximately one third of all cancer cases occurring among children and the leading cause of cancer deaths in children¹. Use of HCT has increased as new techniques have allowed for transplantation in patients who previously would not have been considered HCT candidates. Approximately 30,000 allogeneic HCTs will be performed worldwide in 2020; 20% of allogeneic HCT are performed in the pediatrics population. However, the efficacy of this procedure has been impeded by frequent and severe graft versus host disease (GVHD). The development of GVHD is tightly linked to the beneficial graft versus tumor (GVT) effect, the most potent form of immunotherapy. Nowadays, acute GVHD is measured by clinical symptoms in three organ systems: the skin, liver and gastrointestinal (GI) tract²⁻⁴. Acute GVHD typically occurs between two and eight weeks after transplant, but may occur later⁴, and is often clinically indistinguishable from other causes of clinical symptoms such as conditioning regimen toxicity, infection, or medication. Endoscopic biopsy is often used to confirm the diagnosis^{2,5}, but histologic severity on biopsy has not consistently correlated with clinical outcome^{3,5-7}. A noninvasive, reliable blood biomarker specific for GVHD with strong prognosis information would thus significantly aid in the management of patients with this disorder.

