Predictive Model. If we validate the proteins as diagnostic biomarkers, we will in this next part of the project ask whether this biomarker can be used to predict the future development of GVHD before its clinical signs become manifest. This statistical step will evaluate the value of the composite panel as a screening test for the risk of developing GVHD by computing the positive and negative predictive values. In order to be clinically useful, we expect that both values will be > 75%. In this case, we would expect that the biomarkers will correlate with subclinical disease. This possibility is likely, given that our preliminary data showed that TNFR1 levels in day 7 post- allogeneic transplant plasma

correlates with eventual severity and incidence of GVHD, and with overall survival^{33,34}. We propose to use our novel repository of samples and the clinical data from SA 1 to determine if any of these biomarkers have predictive ability when measured earlier in the patient's course. We are in a unique position to perform this analysis because our bank will contain samples that are collected from patients on a weekly basis during the first month after transplant. We will measure concentrations of the biomarkers at D7, D14, and D21 post- HCT (7 to 21 days prior to the onset of GVHD) and from similar time points in control patients, which will permit the generation of a kinetic curve for the individual biomarker.

We will develop a predictive model using Cox proportional hazard model with time dependent covariates. Time to GVHD development is a time to event outcome, protein biomarkers measured at D7, D14, and D21 post HCT are time dependent covariates, and treatment/control data and other clinical and demographic variables will be time independent covariates. To perform these analyses GVHD onset will be used as the event outcome. The control group includes the patients accrued on this protocol who do not develop GVHD. Two strategies will be used to model the time dependent biomarkers. One strategy is a simple linear interpolation and extrapolation of biomarker measurement to days other than day 7, 14, and 21. The second strategy is to model biomarker with either the linear trend or quadratic trend.

Although these two strategies will pose different Cox regression models with time

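### At the day 21 landmark the NRM analyses do not separate patients who already have acute GVHD from those sampled before onset

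*SAP*

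**What the plan says.** The SAP (Statistical analysis) handles "time-dependent biomarker values (pre-HCT, and at 7, 14 and 21 days post-HCT) we employed landmark analyses". At each landmark, "the biomarker value at this landmark time point was considered and, also, patients who survived until that landmark". Two outcomes share this set-up: "Cumulative incidences of NRM and aGVHD were analyzed with relapse as a competing risk". Curves for the two marker groups are compared "while accounting for the left truncation at each landmark point, we used two-sample nonparametric linear tests". The multivariable model stacks the landmarks and adjusts for "race/ethnicity, malignant disease, graft source, and aGVHD prophylaxis". It includes a biomarker-by-landmark interaction, which the SAP reads as change over time in the association between marker and outcome. GVHD status at the landmark is not a covariate, and no analysis in GVHD-free patients is described.

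The protocol supplies the timing. Section 1.1 states: "Acute GVHD typically occurs between two and eight weeks after transplant, but may occur later". The sample-size paragraph of Appendix C places early sampling "at day 14 post-HCT (median 14 days prior GVHD" onset. Its Predictive Model paragraph asks "whether this biomarker can be used to predict the future development of GVHD before its clinical signs become manifest" and describes the day 7, 14 and 21 samples as falling 7 to 21 days ahead of onset. Secondary objective 1 (Section 2.1) asks whether day 14 or day 21 markers predict day 180 post-transplant NRM, and sets no GVHD-free condition.

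**The concern.** A day 21 sample can come from a patient who has not yet developed GVHD or from one who already has it. The protocol's preliminary data (Section 1.3) show that active GVHD moves at least two of the SAP's four markers: REG3α is higher in patients with GVHD than without, and TNFR1 fell in patients whose GVHD resolved. The same section links GVHD grade at onset to NRM (20% for grades 1-2, 50% for grades 3-4). GVHD status at the landmark is therefore plausibly related to both marker and outcome.

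The stake is interpretation. A marker that rises only once GVHD has begun could show some association with NRM at day 21 without containing any pre-onset information. Because prevalent GVHD goes from almost none at day 7 to a material share at day 21, the biomarker-by-landmark interaction could partly reflect a changing patient mix.

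**Working it through.** The documents give no count of GVHD before each landmark, so there is no stated figure to reproduce. What follows is an illustration.

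**Inputs from the documents**
- Usual onset: weeks 2 to 8, that is days 14 to 56 (Protocol 1.1).
- Implied median onset: 14 + 14 = day 28 (Appendix C). The 7-to-21-day description fits only this onset day, since 28 − 21 = 7 and 28 − 7 = 21.
- Sampling window up to day 28: ±4 days (Table 3 footnote), so the day 21 sample may fall as late as day 25.
- Cohort: 415 (SAP). GVHD rate 0.50 and post-therapy NRM 0.26 (power table, Appendix C).

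**Assumed:** log-normal onset with median 28, and days 14 to 56 holding the central 95%, 90% or 80% of onsets. Since 28/14 = 56/28 = 2, the log-scale SD is s = ln 2 / z, with z = 1.960, 1.645 or 1.282, giving s = 0.354, 0.421 or 0.541.

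**Share of GVHD already begun by day d:** Φ(ln(d/28)/s). Patients = 415 × 0.50 × share.

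| Sampling day | Share of cases (95% / 90% / 80%) | Patients of 415 |
|---|---|---|
| 7 | at most 0.5% | about 1 or fewer |
| 14 | 2.5% / 5% / 10% | 5 / 10 / 21 |
| 21 | 21% / 25% / 30% | 43 / 51 / 62 |
| 25 (late edge) | 37% / 39% / 42% | 78 / 82 / 87 |

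As a share of the cohort, day 21 gives 43/415 = 10% to 62/415 = 15%, and day 25 gives 78/415 = 19% to 87/415 = 21%. If incidence were 0.30 (assumed), the day 21 count would be 26 to 37.

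**Possible effect on NRM at day 21.** Take a marker with no pre-onset information that rises by 0.5 to 1.5 SD after onset, split at the median. Let NRM be 0.26 with GVHD and 0.10 without (the latter assumed).

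Upper case: prevalent share 0.149 and shift 1.5 SD, so 91% of prevalent cases are marker-high.
- NRM in everyone else: (0.351 × 0.26 + 0.50 × 0.10)/0.851 = 0.166.
- Share of everyone else who are marker-high: (0.5 − 0.149 × 0.91)/0.851 = 0.428.
- High group: (0.149 × 0.91 × 0.26 + 0.851 × 0.428 × 0.166)/0.5 = 0.191.
- Low group: (0.149 × 0.09 × 0.26 + 0.851 × 0.572 × 0.166)/0.5 = 0.169.
- Risk ratio: 0.191/0.169 = 1.13.

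Lower case: prevalent share 0.104 and shift 0.5 SD gives a ratio of 1.04. The same calculation gives 1.00 to 1.04 at day 14 and 1.00 at day 7.

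Harsher assumptions (70% to 90% of prevalent cases marker-high; NRM 0.05 to 0.15 in all others; 12% to 15% prevalent) give 1.07 to 1.90 at day 21. The top of that range needs both 90% marker-high and 5% NRM elsewhere, and neither figure is in the documents.

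**The case against.** The strongest reply has four parts.

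1. A reader might infer that patients with earlier GVHD are counted as later aGVHD events. The text does not support this. The SAP accounts for left truncation when comparing the aGVHD curves, and a first aGVHD before the landmark precedes entry. Relapse before the landmark is excluded by the same logic. What stands is a wording gap: the entry sentence names survival alone, and left truncation is mentioned for the two-sample tests but not for the stacked model.

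2. A reader might infer that the all-survivor NRM analysis is wrong. It is not: it matches secondary objective 1. The aim of predicting before clinical signs is stated for GVHD development in Appendix C, and the SAP makes no such claim for NRM. This stands, so the additional analyses supplement the existing one.

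3. A reader might treat day 14 as equally affected, or conclude that the study cannot support any use of the markers before symptoms. Under the assumptions above, the pre-transplant, day 7 and day 14 landmarks are nearly unaffected.

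4. The day 21 effect may be small. For ratios of 1.04 to 1.13 with 415 patients, a simple two-sided 5% comparison of proportions would reject about 5% to 9% of the time. The 0.26 is a post-therapy rate used here for post-transplant NRM, and the 0.50 is a planning input.

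It is also tempting to say that prevalent cases were on systemic steroids. That is inferred from the protocol's link between the onset sample and steroid-triggering symptoms; the SAP does not mention steroids.

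**Conclusion.** The concern holds in a limited form, mainly for NRM at day 21. The survival-only entry rule and the absence of landmark GVHD status from the covariates are plain in the text. On the assumed onset distribution, 21% to 30% of cases (43 to 62 of 415 patients at 50% incidence) are already present by day 21, against 2.5% to 10% by day 14. The day 21 NRM association therefore mixes prognosis before onset with prognosis in established GVHD, and the change in mix across landmarks can contribute to the biomarker-by-landmark interaction, by an amount not quantified here. The risk ratio attributable to prevalent cases alone could be as low as 1.04 to 1.13; larger values need stronger assumptions. The documents do not show that the NRM results are invalid. They do show that the planned analysis cannot, on its own, carry a claim about prediction before GVHD signs.

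**What to change.** - Keep the NRM analysis in all landmark survivors, as the answer to secondary objective 1.
- Add a stacked NRM model with aGVHD status at the landmark as a covariate.
- Repeat the NRM analysis in patients who were aGVHD-free at sampling, and rest any pre-onset claim on that restricted analysis.
- For aGVHD, replace the survival-only wording with alive, relapse-free and aGVHD-free at the landmark, consistent with the left truncation already stated.
- Report the number with prevalent aGVHD at each landmark.

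The data should exist: Section 3.3 lists the day of acute GVHD onset, and Table 3 schedules an acute GVHD evaluation at days 7, 14 and 21. The cost is SAP wording, one extra model per marker, and a smaller restricted day 21 analysis: about 10% to 15% fewer patients, or up to about 21% if samples fall at the late edge of the window. The SAP is dated February 2020, after accrual ended in 2018, so these analyses should be labelled as additions.

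### The SAP applies p<0.05 throughout and does not mention the protocol's 0.0012 level for its primary comparisons; at most three of at least 32 landmark tests conflict directly, and the rest have no stated status.

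*SAP*

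**What the plan says.** **Protocol, Appendix C, Sample Size and Power Calculation.** "Three clinical endpoints are chosen as the primary hypotheses": non-relapse mortality (NRM) at day 180 after therapy, non-response at day 28 after therapy, and GVHD grade 1-4 onset. "Seven biomarkers will be tested at either onset of GVHD or at day 14 post-HCT". Multiplying 7 markers, 3 endpoints and 2 time points gives 42, and so "the per comparison type I error is controlled at 0.05/42 = 0.0012".

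**Protocol, sections 2.1 and 3.1.** The primary objective concerns markers measured when GVHD therapy starts. Day 14 and day 21 markers against day-180 post-HCT NRM form secondary objective 1, which names ST2 alone or the seven-marker panel. No alpha is given for it.

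**Protocol, Appendix C, Predictive Model.** If the proteins are validated as diagnostic markers, a Cox model for time to GVHD will use day 7, 14 and 21 values as time-dependent covariates. Again no alpha is given.

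**SAP.** "ST2, IL6, REG3α, and TNFR1 were measured pre-HCT (day -7) and on days +7, +14, +21 post-HCT". "Cumulative incidences of NRM and aGVHD were analyzed with relapse as a competing risk". Patients are split by marker category at each landmark, and to compare the curves "we used two-sample nonparametric linear tests". A stacked cause-specific hazards model adds marker-by-landmark and marker-by-age interactions, and there is a separate analysis in malignant disease. Hazard ratios with confidence intervals are reported. The closing rule is "A p-value of <0.05 was considered significant".

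**The concern.** The protocol set a demanding criterion for its primary comparisons, and the SAP neither carries it over nor says why it was dropped. Where a SAP test is also one of the 42, it is judged at a level 42 times looser, so a day-14 marker could be called significant without meeting the protocol's own criterion.

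The second problem is wider but softer. One rule covers comparisons that the protocol planned and comparisons that it did not, such as those for IL6, which is not among the seven panel markers listed in protocol section 2.1. The SAP text alone does not separate the two kinds. Reporting hazard ratios with confidence intervals shows effect size, but it does not control error or say which results are confirmatory.

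**Working it through.** **Inputs.** From protocol Appendix C: 7 markers, 3 endpoints, 2 time points, N = 350, sensitivity = specificity = 0.60 to 0.70, event rates 0.26, 0.41 and 0.50, and stated power 0.91, 0.96 and 0.98 at 0.60. From the SAP: 4 markers, 4 landmarks, 2 outcomes, threshold 0.05, 415 recipients. Neither document states sidedness, so two-sided tests are assumed.

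**1. The protocol's alpha.** 0.05/(7 × 3 × 2) = 0.05/42 = 0.00119, which rounds to 0.0012. The figure reproduces. Ratio of thresholds: 0.05/(0.05/42) = 42.

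**2. Number of landmark tests in the SAP.** 4 × 4 × 2 = 32. The SAP gives no count, so this is derived. It is a minimum, since interaction, stacked-model and subgroup tests come on top.

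**3. Overlap with the 42.** A SAP test must match on marker, time point and endpoint.
- Marker: ST2, REG3α and TNFR1 are in the panel; IL6 is not.
- Time point: only day 14 is shared; days -7, +7 and +21 are not in the family.
- Endpoint: aGVHD can match GVHD grade 1-4 onset. The SAP states no grade and treats aGVHD as time-to-event with relapse competing, so the match is an assumption. The protocol's primary NRM runs from start of GVHD therapy, whereas the SAP follows landmark cohorts after HCT, so NRM does not match.

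Overlap: 3 × 1 × 1 = 3 at most. The remainder is 32 − 3 = 29.

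**4. Chance of at least one false positive if every null holds**, 1 − (1 − α)^k under independence:

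| Tests | α = 0.05 | α = 0.05/42 |
|---|---|---|
| k = 3 | 1 − 0.95³ = 0.143 | 0.0036 |
| k = 32 | 1 − 0.95³² = 0.806 | 0.037 |

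The tests share patients and markers, so independence gives upper-end values. The documents report no correlations. Under assumed correlations from 0.3 to 0.9 across landmarks and 0.2 to 0.6 across markers and outcomes, simulation gives 0.77 down to 0.40 for the 32 tests at 0.05.

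**5. Power cost, in the protocol's two-proportion setting.** With event rate r, n₁ = N·r, n₂ = N·(1 − r), p₁ = sensitivity, p₂ = 1 − specificity and p̄ = (n₁p₁ + n₂p₂)/N:

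power = Φ{[(p₁ − p₂) − z·√(p̄(1 − p̄)(1/n₁ + 1/n₂))] / √(p₁(1 − p₁)/n₁ + p₂(1 − p₂)/n₂)}

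with z = 1.960 at 0.05 and about 3.241 at 0.05/42.

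Example, N = 415, r = 0.50, sensitivity = specificity = 0.60: null SE 0.0491, alternative SE 0.0481.
- At 0.05: (0.2 − 1.960 × 0.0491)/0.0481 ≈ 2.16, power 0.98.
- At 0.05/42: (0.2 − 3.241 × 0.0491)/0.0481 ≈ 0.85, power 0.80.
- At 0.65 and 0.05/42, power is above 0.99.

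**6. The protocol's power table, N = 350, sensitivity = specificity = 0.60.**

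| Event rate | Stated | Two-sided 0.05 | Two-sided 0.05/42 |
|---|---|---|---|
| 0.26 | 0.91 | 0.91 | 0.52 |
| 0.41 | 0.96 | 0.96 | 0.67 |
| 0.50 | 0.98 | 0.97 | 0.70 |

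The stated row fits about 0.05, not 0.0012. One-sided 0.05/42 does not recover it either (0.60, 0.74, 0.76).

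**The case against.** The best defence is that the SAP reports a different analysis, to which the 42-test rule was never meant to apply. Much of this stands. If the SAP's aGVHD is not the protocol's GVHD endpoint, no landmark test conflicts with 0.0012. The protocol is also not uniform: its primary objective covers only markers at the start of GVHD therapy, and day 14 enters the primary family only through the sample-size paragraph. The power table does not fit 0.0012, so the protocol never reconciled that level with its own design. Holding three tests to 0.05/42 also charges them for 39 comparisons that this SAP does not describe. The sponsor may therefore have a sound case for another level. None of this removes the gap: the SAP does not make that case and names no primary or exploratory tests.

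Three stronger readings are tempting, and the documents do not support them.

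- **All 32 tests should have met 0.0012.** The protocol attaches that level only to the 42 primary comparisons. Secondary objective 1 and the predictive model have no stated alpha.
- **Day-14 NRM also conflicts, making six.** The protocol's primary NRM is counted from GVHD therapy. The SAP's post-HCT NRM is closer to secondary objective 1.
- **The threshold was relaxed after results were seen.** The SAP is dated February 2020, is written in the past tense and reports that "The study accrued 415 HCT recipients between 2013 and 2018". It says nothing about when or why 0.05 was chosen.

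Nor can the other 29 tests be sorted into fixed protocol families for a further correction. Secondary objective 1 names ST2 or the panel, not REG3α and TNFR1 singly. The predictive model is one conditional time-dependent Cox model, not separate tests by day.

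**Conclusion.** The SAP's significance rule is wrong as written and should be corrected, but the direct contradiction is small: at most three tests, conditional on the endpoint match. For those three the threshold is 0.05 against 0.0012, with an illustrative null error of 14.3% against 0.36% under independence. For the other 29 landmark tests, and for the interaction, stacked-model and subgroup tests, the SAP contradicts no protocol alpha. The fault there is that confirmatory, planned and added results are not distinguished. The 81% figure rests on a complete null and independence; it shows why labels are needed and does not estimate this study's actual error rate. The textual conflict depends on none of these rates.

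**What to change.** In the SAP's Statistical analysis section, replace the closing p<0.05 sentence with the following.

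1. State whether aGVHD is the protocol's GVHD grade 1-4 onset. If it is, call the day-14 ST2, REG3α and TNFR1 tests against aGVHD confirmed only at 0.05/42 = 0.0012, or state and justify the departure. If it is not, say that none of the landmark tests is a protocol primary comparison.
2. Label each result by origin: the Appendix C primary family; secondary objective 1 (ST2 or the panel at day 14 or 21 against NRM); the Appendix C predictive model; or not in the protocol (IL6, day -7, day-7 NRM). Give everything outside the primary family, including interaction and subgroup tests, with estimates, confidence intervals and nominal p-values described as unadjusted for multiplicity and not confirmatory.
3. Note beside the rule that the protocol's stated power corresponds to about two-sided 0.05, so readers do not take 0.91 to 0.98 as the power at 0.0012.

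**Cost.** Wording, labels and re-flagged p-values, with no new samples or assays. Fewer results can be called confirmed. For the three tests, at the weakest stated effect (0.60) and N = 415, power falls from 0.98 to 0.80; at 0.65 it stays at 0.99 or more. These figures use the protocol's two-proportion setting and only approximate the landmark tests.
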